1.1 Frequency of intervention

4 times

1.2 Duration and intensity of intervention

60 minutes/time, once in each of the 1st, 3rd, 5th and 8th weeks of the intervention period.

1.3 Intervention format

group intervention, 12 people in a group (in principle, no more than 15 people).

1.4 Intervention content

The content of health education includes (1) fall risk and preventability in the elderly (2) improving the home environment to prevent falls (3) identifying environmental risk factors in the community and public places (4) changing fall-prone behaviours.

See Table 2 for specific content.

1.5 Intervention tool

accompanying teaching materials (PPT)

1.6 Intervention providers

the intervention was completed by trained staff of the community health service centres in the project area, with at least two staff members required in each community, one staff member acting as the health education activity group leader, who was mainly responsible for organising and implementing each health education group activity (lecturing, organising discussions, teaching exercise movements, answering questions from the study participants, and generally arranging the group's activities); the other staff member As an assistant, the other staff member worked with the group leader to implement the group activities, and visited and protected the study participants during the exercise period.

(2) Strategy 2: Development of individual exercise skills:

2.1 Frequency of intervention

4 times

2.2 Duration and intensity of intervention

30 minutes/time, once in each of the 1st, 3rd, 5th and 8th weeks of the intervention period.

2.3 Intervention format

group intervention, 12 people in a group (in principle, no more than 15 people).

2.4 Intervention content

The content of health education included (1) basic knowledge of exercise safety, 4 methods of balance function exercise (2) review of 4 methods of balance function exercise (3) methods of exercising muscle strength (4) 2 methods of endurance exercise. See Table 3 for specific content.

2.5 Intervention tool

accompanying teaching text (PPT)

2.6 Intervention providers:

same as before.

Table 2 Time, frequency and main content of the implementation of the 4 fall prevention education courses

Number of group activities	intervention time	Key knowledge skills
First time	Week 1	Fall risk and preventability in the elderly
Second time	Week 3	Improving the home environment to prevent falls
Third time	Week 5	Identify environmental risk factors in communities and public places
Fourth time	Week 8	Change behaviours that predispose to falls. Reviewing skills and exercises that have already been learnt

Table 3 Time, frequency, and main content of 4 development of individual exercise skills

Number of group activities	intervention time	Key knowledge skills
----------------------------	-------------------	----------------------

First time	Week 1	Basic knowledge of exercise safety 4 methods of exercising balance function
Second time	Week 3	Reviewing learned exercise methods 4 methods of exercising balance function
Third time	Week 5	Reviewing learned exercise methods 3 ways to build muscle strength
Fourth time	Week 8	2 endurance exercise methods Reviewing learned exercise methods

(3) Strategy 3: Environmental assessment

3.1 Duration and intensity of intervention:

The integrated intervention group and the environmental intervention group community implemented 1 home falls environmental risk factor assessment and modification guidance for the intervention group study participants in the 6th week after the start of the health education group activities.

3.2 Intervention method, intervention content and intervention tools:

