The study subjects were grouped in a completely randomised manner, with a statistician independent of the research team using a computer to generate random numbers, and equal proportions of the study subjects recruited from the 24 streets (towns) were allocated to the 8 experimental condition groups, so that each experimental condition contained all the study subjects from 3 streets (towns). After grouping was completed, a database of basic information about the study participants was created, as shown in Table 1. This study was blinded only to the data collectors and data analysers.

Table 1 Subgroups of the Community Falls Prevention for Older People Pilot Project

groups	Fall Prevention Education Course	Development of personal exercise skills	Environmental assessment
Group 1	Yes	Yes	Yes
Group 2	Yes	Yes	No
Group 3	Yes	No	Yes
Group 4	Yes	No	No
Group 5	No	No	No
Group 6	No	Yes	Yes
Group 7	No	Yes	No
Group 8	No	No	Yes

IV. Intervention Strategies

(1) Strategy 1: Falls prevention education programme

To organise the research subjects in the intervention group to set up a fall prevention health education activity group, in which the project team will disseminate knowledge and concepts of fall prevention through lectures, discussions, questions and answers, and sharing, so as to enhance the knowledge base required by the research subjects to prevent falls and to cultivate the relevant concepts.

(2) Strategy 2: Developing personal exercise skills

Through lectures, demonstrations, on-site exercises and practices, the project team taught the intervention group participants to improve their balance function, lower limb muscle strength, endurance exercise and other fall prevention exercise skills, and to use fall prevention aids through group activities.

(3) Strategy 3: Environmental Assessment

Through the staff's home assessment and guidance, the project team instructed the study participants to assess the risk factors of fall-related home environment and made suggestions for modification.

V. Main intervention activities

(1) Strategy 1: Fall prevention education programme:

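### Table 2 puts a review of exercises in education session 4; read literally, Groups 1 and 2 get exercise review inside the education factor and Groups 6 and 7 do not

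*Combined protocol and SAP*

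**What the plan says.** Section IV (1) defines Strategy 1, the education course. The project team is to "disseminate knowledge and concepts of fall prevention through lectures, discussions, questions and answers, and sharing". Exercise is taught under Strategy 2.

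Section V (1) 1.4 gives four education topics, none of them exercise. The last two read "identifying environmental risk factors in the community and public places (4) changing fall-prone behaviours". It then adds "See Table 2 for specific content", so Table 2 carries the detailed content. In Table 2 the Week 8 entry has behaviour change and, after it, "Reviewing skills and exercises that have already been learnt".

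Table 3, for the exercise strategy, has its own review in the same week: "2 endurance exercise methods Reviewing learned exercise methods".

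The two strategies share a calendar. Education sessions are "60 minutes/time, once in each of the 1st, 3rd, 5th and 8th weeks of the intervention period" and exercise sessions are "30 minutes/time, once in each of the 1st, 3rd, 5th and 8th weeks of the intervention period".

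By Table 1 in Section III (3), Groups 1 and 2 receive both education and exercise, Groups 3 and 4 education without exercise, and Groups 6 and 7 exercise without education.

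**The concern.** The trial exists to separate components that the earlier programme delivered as a bundle. Section I says that the contribution of each element could not be confirmed then, and Section II sets out to screen the elements. That requires the education factor to contain only education, so that adding it to the exercise component changes nothing else.

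The Table 2 line does not respect that boundary. Someone running education session 4 in Group 1 or 2 could fairly read it as an instruction to go over the physical exercises again. Groups 6 and 7 have no education session in which this could happen. Part of any benefit from extra exercise practice would then be credited to education, in a trial whose results may decide which component is dropped.

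**Working it through.** The plan gives no figure on this point. The check is which groups the line can reach, and how an effect there would pass into the factorial comparisons.

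**Inputs.** Group coding: Table 1. Group size 111, total 888: Section III (2). Three streets per group, 24 in all: Section III (3). Session lengths and numbers: Section V (1) 1.1–1.2 and (2) 2.1–2.2.

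**Who can receive an extra review.** It takes education (to be in the session) and exercise (to have something to review).
- Groups 1 and 2 have both, so exposure is possible.
- Groups 3 and 4 attend the session but have learnt no trial exercises. Exposure is taken as nil.
- Groups 6 and 7 have exercise, including the reviews in Table 3, but no education session.
- Groups 5 and 8 have neither.

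**Reach, as a ceiling.** People: 2 × 111 = 222 of 888 (25%). Streets: 2 × 3 = 6 of 24. Sessions: 1 of 4 in the education course.

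**Dose.** Scheduled exercise contact is 4 × 30 = 120 minutes in each of Groups 1, 2, 6 and 7. Education session 4 lasts 60 minutes and must also cover behaviour change, so an extra review would take less than 60 minutes. The split is not given, and zero is possible.

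**Effect on the comparisons.** Let e be the effect of the extra review on an additive scale, present in Groups 1 and 2 only. Each main effect is the mean of four pairs that differ in one factor.

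| Factor | Pair and contribution | Mean |
|---|---|---|
| Education | 1 vs 6: e; 2 vs 7: e; 3 vs 8: 0; 4 vs 5: 0 | 2e/4 = e/2 |
| Exercise | 1 vs 3: e; 2 vs 4: e; 6 vs 8: 0; 7 vs 5: 0 | 2e/4 = e/2 |
| Environment | 1 vs 2: e − e = 0; 3 vs 4: 0; 6 vs 7: 0; 8 vs 5: 0 | 0 |

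The education-by-exercise difference of differences would take e − 0 = e. If e = 0, every entry is zero.

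The documents give no basis for the effect of a single review on falls, so e is left as a symbol.

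**Does another section settle it?** No. Section IX (5) 5.2 bars people from attending other groups' activities, but this concerns a group's own session. Section IX (3) 3.1–3.2 standardises materials and training without saying which content belongs to which factor.

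**The case against.** The best reply is that the two tables describe one review. Both strategies run in the same four weeks, in groups of the same size, with the same providers (Section V (2) 2.6 refers back to the education text). For Groups 1 and 2 the Week 8 review could simply be listed twice, and then e = 0. This stands as a live reading, but the plan does not say that it is the right one.

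A second reply is that the silence of Section V (1) 1.4 on exercise review proves little, because the content lists are brief. Section V (2) 2.4 likewise leaves out reviews that Table 3 shows for sessions 3 and 4. This also stands. The case therefore rests on the Strategy 1 definition and on Table 2 being named as the detailed content.

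Third, the English reads as a translation, and the word exercises could mean practised course material. The teaching slides and the manuals, which would show this, are not included. That is possible, and one added phrase would settle it.

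Fourth, a factorial trial estimates components as delivered, and something possible only when both are given belongs to the combination. That is fair for comparing whole packages. It does not help when the education effect is read as that of knowledge and concepts alone.

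A reader might infer more from the provider text in Section V (1) 1.6, which lists "lecturing, organising discussions, teaching exercise movements, answering questions from the study participants" among the group leader's duties. That does not show exercise being taught in education sessions. Strategy 2 relies on the same paragraph for its providers, so it is best read as a shared duty list. Nor should one infer that Groups 3 and 4 received exercise content, since they had none to review.

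**Conclusion.** The point holds as a wording problem that touches the separation of factors, at low severity. Table 2, to which the plan itself defers, places exercise review in the education course, against the definition of that strategy and alongside a review already scheduled in Table 3. Taken literally, Groups 1 and 2 receive something inside education that Groups 6 and 7 do not, and e/2 enters both the education and the exercise main effects.

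This rests on three assumptions: the two table entries are separate reviews, the word means physical exercise, and effects add. The first two are uncertain. The overlap is possible and probably small, with a ceiling of a quarter of participants in one of four education sessions.

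A reader might conclude that the education estimate is biased, or that a planned interaction test is distorted. The documents support neither. The dose is unstated and may be zero, and Section VII plans only t-tests and chi-square tests between groups, with no interaction analysis.

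**What to change.** In Table 2, session 4, delete the exercise review and limit the line to review of the education content. Leave exercise review to Table 3, which already schedules it in Week 8 for Groups 1, 2, 6 and 7. If the line never meant physical exercise, saying so in the table does the same job.

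If Week 8 sessions have already been held, state in the report what was delivered in education session 4 in Groups 1 and 2, and take it into account when interpreting the education effect.

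The cost is one table line, with no change to sessions, staff or sample size. Marking the exercise duties in Section V (1) 1.6 as applying to Strategy 2 sessions would be tidier, but it is optional and the point does not depend on it.

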3.2.1 Intervention content

①Assessment of environmental risk factors for falls in the indoor environment of the homes, hallways, or courtyards where the elderly people live on a daily basis;

②Provide in-person guidance on the environmental risk factors found and fill out two written environmental assessment and modification recommendations, one to be filled out by the investigator and then filed and entered; the other record to be left for the use of the respondents;

③ Provide at least the services of a night light, bathroom non-slip mats, fall prevention warning signs, and double-sided adhesive fixed carpet floor mats. Conditional areas are encouraged to provide more retrofitting services.

3.2.2 Intervention Methods

After making an appointment, the project staff will enter the households at the agreed time to conduct fall risk assessment of the study subject families in the intervention group.

3.2.3 Intervention Tools

When carrying out the guidance on assessing the risk factors for falls in the home environment, project staff mainly used the "Risk Factors for Falls in the Home Environment of the Elderly and Suggestions for Retrofitting" (Appendix 4) to carry out the assessment on an article-by-article basis and to provide suggestions for retrofitting. Other intervention tools included night lights, non-slip mats, fall prevention warning signs, double-sided tape, and other tools.

3.3 Intervention providers

Trained project community social workers or CHC staff.

3.4 Implementation Records

When carrying out the home environment risk assessment, with the consent of the study participants, record the time of the assessment, the participants, the assessment process, the assessment results, and the guidance suggestions using pictures, videos, and words, and fill in the "Record of Home Environment Assessment and Improvement Form" (Appendix 8); special attention is paid to the collection of comparisons before and after the environmental modification.

VI. Project evaluation

Project evaluation includes baseline survey evaluation, effectiveness evaluation and

economics evaluation.

(1) Baseline survey assessment

1.1 Pre-intervention status of research subjects (baseline survey)

1.1.1 Implementation time

May 2024-June 2024.

1.1.2 Subjects of the survey

All older adults in the 8 study groups.

1.2 Baseline survey assessment content

1.2.1 Basic demographic information

Name, gender, age, address, contact information, ethnicity, cohabitation, occupational status, and education level.

1.2.2 Physical activity

Daily physical activity.

1.2.3 Illness and medication status

Type and number of illnesses, type and number of medications.

1.2.4 Falls-related information

Specific information on the occurrence of falls in the past year, fall effectiveness level.

1.2.5 Assessment methods and tools

① Assessment methods

Questionnaire survey, on-site observation and other methods are selected according

to different assessment contents.

② Assessment tools

Self-administered questionnaire: basic demographic information, physical activity, illness and medication use, and occurrence of falls (occurrence of falls in the last year);

Established scale measurements: Falls Effectiveness Scale for the Elderly, Quality of Life Scale.

See Annex 5 for specific assessment methods and tools.

Table 4 List of project baseline survey and assessment contents, methods and tools

Content		Method	Tool
classification	item		
Basic demographic information	Name, sex, age, address, contact details, ethnicity, level of education, living with the family, occupational status	Survey	Annex 5: Survey Assessment Form (Part I)
Illness, Medication and Medical conditions	Type and number of illnesses, type and number of medicines used	Survey	Annex 5: Survey Assessment Form (Part II)
Information about falls	Incidents of falls, history of falls	Survey	Annex 5: Survey Assessment Form (Part III)
	Falls Related Knowledge, Attitude and Action	Survey	Annex 5: Survey Assessment Form (Part IV)
	Falls efficacy	Scale	Annex 5: Survey Assessment Form (Part V)
Quality of Life Scale	Capacity for daily living	Scale	Annex 5: Survey Assessment Form (Part VI)
Gait	"Stand-up-and-walk" timing test	on-site test	Annex 5: Survey Assessment Form (Part VI I)

1.2.6 Main Evaluation Indicators

① Indicators reflecting the occurrence of falls: rate of people falling (number), rate of people falling (number), rate of people falling (number), rate of people falling

(number), rate of people falling (number), and rate of people falling (number).

The rate of people falling (number), the rate of people falling (number), the rate of people falling (number), the rate of people falling (number).

② Reflecting the effectiveness of falls: the score of the Falls Effectiveness Assessment Scale.

③ Reflecting the ability to perform daily living tasks: score on the Quality of Life Scale.

(2) Process evaluation (intervention phase)

2.1 Evaluation time

May 2024-November 2024 (the whole process of project implementation)

2.2 Assessment Objects

Research subjects, project team staff.

2.3 Assessment contents and methods

2.3.1 Completion of group activities of research subjects

Evaluation of group activity attainment. The intervention team calculates the group activity attendance rate of the research subjects based on their attendance in the group activity record (number of research subjects who actually participated and completed the current group activity/number of research subjects who should have participated in the current group activity $\times 100\%$). The record form is shown in Appendix 3, "Record Form of Research Subjects' Participation in the Project Process".

2.3.2 Quality of the organisation and implementation of intervention activities

On-site assessment team of CDC institutions at municipal and district levels, selecting at least 30% of group activities for on-site quality assessment (on-site listening), required to cover all 4 activities and at least 50% of intervention communities, focusing on understanding the quality of the implementation of group activities and the learning effect of the elderly. The on-site assessment should cover all intervention groups. For details of the recording tool, please refer to Annex 6 "On-site quality assessment form for group activities

2.3.3 Satisfaction of study participants with group activities

① Groups 1, 2, 3, 4, 6 and 7 Intervention Communities Each community, after completing the health education group activities, organises a satisfaction survey and group interviews with the study participants to find out the satisfaction, feelings and suggestions of the study participants in participating in the group activities. For details of the recording tools, see Annex 7, "Intervention Participants' Satisfaction Survey Form (Elderly)".

② After the completion of household environmental assessment, guidance and improvement in the intervention community, ask for their satisfaction and record it in Annex 8, "Record Sheet for Household Environmental Assessment and Improvement Guidance".

2.3.4 Household guidance and assistance in environmental improvement

Evaluate the implementation of guidance and assistance in completing the environmental modification of household risk factors for study participants who have been admitted to households. Based on the record of household visits, calculate the completion rate of household guidance and assistance in environmental modification

(number of households actually visited and completed guidance and assistance in environmental modification / number of households that should be visited for guidance and assistance in environmental modification x 100%). For the record sheet, please refer to Annex 8 "Record Sheet for Household Environmental Assessment and Improvement Guidance Work".

2.4 Assessment Tools

Different assessment tools such as observation record sheets, questionnaires, interview outlines, etc. were selected and used according to the different contents and methods of the process assessment, as detailed in Table 5.

Table 5 List of project process evaluation contents, methods and tools

Content	Subject	Method	Tool
1. Completion rate of group activities by study participants	Study subjects in the intervention group	on-site observation	Record of Participation of Research Subjects in the Project Process (Annex 3)
2. Quality of the organisation and implementation of the intervention	Implementation team activities staff	on-site observation	Panel activity site quality assessment form (annex 6)
3. Satisfaction of study participants with group activities	Study subjects in the intervention group	Survey	Project Activity Satisfaction Questionnaire (Elderly) (Annex 7)
4. Household guidance and assistance in environmental rehabilitation	Staff implementing guidance on environmental improvements to households	Summary of work records	Household Environmental Assessment and Improvement Guidance Record Sheet (Annex 8)

(3) Assessment of effects

It is proposed to study the effect of the intervention at 6 and 12 months after the start of the intervention. The assessment of the occurrence of falls will be collected by filling in the monthly fall calendar; the changes in fall efficacy, knowledge, beliefs and

behaviours will be collected through on-site survey and testing.

3.1 Data collection on the occurrence of falls in the study population

3.1.1 Assessment subjects

All study subjects in the 8 study groups.

3.1.2 Assessment period

From May 2024 to May 2025, information on the occurrence of falls was collected on a monthly basis during the period from the start of the intervention to the completion of 12 months of the intervention.

3.1.3 Assessment content

Basic information on the occurrence of falls, with the same content as the baseline survey and assessment.

3.1.4 Assessment methods and tools

① Study participants use the Monthly Record of Falls Occurrence Calendar (Appendix 9) to record whether a fall has occurred or not.

Staff collected the Monthly Falls Record Calendar on a monthly basis, and used the Baseline Survey Questionnaire on the Occurrence of Falls among the Elderly (Annex 5, Part III) to conduct a detailed investigation on the time of falls that occurred.

3.2 First Effectiveness Assessment (after the start of the first intervention, at the completion of 6 months)

